8.1.1. Permanent Discontinuation from Study Treatment

Possible reasons leading to permanent discontinuation of investigational product:

- Participant decision:
 - the participant or the participant's designee, for example parents or legal guardian, requests to discontinue investigational product.
- Discontinuation due to a hepatic event or liver test abnormality. Participants who are discontinued from investigational product due to a hepatic event or liver test abnormality should have additional hepatic safety data collected via the hepatic safety eCRF.
- Discontinuation of the investigational product for abnormal liver tests should be considered by the investigator when a participant meets one of the following conditions after consultation with Lilly Medical.
- In study participants with normal or near normal baseline liver tests (ALT, AST, ALP $<1.5 \times$ ULN), the study drug should be **interrupted** and close hepatic monitoring initiate (see [Appendix 4](#)) if one or more of these conditions occur:

Elevation	Exception
ALT or AST $>8 \times$ ULN	
ALT or AST $>5 \times$ ULN for more than 2 weeks	
ALT or AST $>3 \times$ ULN and either TBL $>2 \times$ ULN or INR >1.5 $<1.5 \times$ ULN	For participants with Gilbert's syndrome: If baseline direct bilirubin is >0.5 mg/dL, then doubling of direct bilirubin should be used for drug interruption decisions rather than TBL $>2 \times$ ULN.
ALT or AST $>3 \times$ ULN with the appearance of fatigue, nausea, vomiting, right upper quadrant pain or tenderness, fever, rash, and/or eosinophilia ($>5\%$)	
ALP $>3 \times$ ULN, when the source of increased ALP is the liver	
ALP $>2.5 \times$ ULN and TBL $>2 \times$ ULN	For participants with Gilbert's syndrome: If baseline direct bilirubin is >0.5 mg/dL, then doubling of direct bilirubin should be used for drug interruption decisions rather than TBL $>2 \times$ ULN.
ALP $>2.5 \times$ ULN with the appearance of fatigue, nausea, vomiting, right upper quadrant pain or tenderness, fever, rash, and/or eosinophilia ($>5\%$)	

Abbreviations: ALP = alkaline phosphatase; ALT = alanine aminotransferase; AST = aspartate aminotransferase; INR = international normalized ratio; TBL = total bilirubin level; ULN = upper limit of normal.

Source: FDA Guidance for Industry: Drug-Induced Liver Injury: Premarketing Clinical Evaluation, July 2009 and other consensus guidelines, with minor modifications.

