Interrupting study drug based on elevated liver tests in participants with abnormal baseline liver tests

- In study participants with abnormal baseline liver tests (ALT, AST, ALP $\geq 1.5 \times$ ULN), the study drug should be **interrupted** if one or more of these conditions occur:

Elevation	Exception
ALT or AST $>4 \times$ baseline	
ALT or AST $>3 \times$ baseline for more than 2 weeks	
ALT or AST $>2 \times$ baseline and either TBL $>2 \times$ ULN or INR >1.5	For participants with Gilbert's syndrome: If baseline direct bilirubin is >0.5 mg/dL, then doubling of direct bilirubin should be used for drug interruption decisions rather than TBL $>2 \times$ ULN.
ALT or AST $>2 \times$ baseline with the appearance of fatigue, nausea, vomiting, right upper quadrant pain or tenderness, fever, rash, and/or eosinophilia ($>5\%$)	
ALP $>2.5 \times$ baseline, when the source of increased ALP is the liver	
ALP $>2 \times$ baseline and TBL $>2 \times$ ULN	For participants with Gilbert's syndrome: If baseline direct bilirubin is >0.5 mg/dL, then doubling of direct bilirubin should be used for drug interruption decisions rather than TBL $>2 \times$ ULN.
ALP $>2 \times$ baseline with the appearance of fatigue, nausea, vomiting, right upper quadrant pain or tenderness, fever, rash, and/or eosinophilia ($>5\%$)	

Abbreviations: ALP = alkaline phosphatase; ALT = alanine aminotransferase; AST = aspartate aminotransferase; TBL = total bilirubin level; ULN = upper limit of normal.

Source: FDA Guidance for Industry: Drug-Induced Liver Injury: Premarketing Clinical Evaluation, July 2009 and other consensus guidelines, with minor modifications.

Resuming study drug after elevated liver tests

- Resumption of the study drug can be considered only in consultation with the Lilly-designated medical monitor and only if the liver test results return to baseline and if a self-limited nondrug etiology is identified. Otherwise, the study drug should be discontinued.

In addition, patients will be discontinued from the study drug under the following circumstances:

- Neutrophil (segmented) counts:
 - <500 cells/ μ L
 - \geq 500 and <1000 cells/ μ L (based on 2 test results; the second test performed within 1 week from knowledge of the initial result)
 - \geq 1000 and <1500 cells/ μ L (based on 3 test results) and an infection that is not fully resolved
 - white blood cell count <1000 cells/ μ L ($1.00 \times 10^3/\mu$ L or 1.00 billion/L)

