Hepatic	
Hepatic AE analysis will include events that are potentially drug-related hepatic disorders by using the MedDRA PTs contained in any of the following SMQs:
 
 • Broad and narrow terms in the Liver related investigations, signs and symptoms (20000008) • Broad and narrow terms in the Cholestasis and jaundice of hepatic origin (20000009) • Broad and narrow terms in the Hepatitis, non-infectious (20000010) • Broad and narrow terms in the Hepatic failure, fibrosis and cirrhosis and other liver damage (20000013) • Narrow terms in the Liver-related coagulation and bleeding disturbances (20000015) 
The number and percentages of patients with the following elevations in hepatic laboratory tests at any time will be summarized between treatment groups:
 
 • The number and percentages of patients with an ALT or AST measurement ≥ 3 times (3\times), 5 times (5\times), 10 times (10\times), and 20 times (20\times) the Performing lab ULN during the treatment period will be summarized for all patients with a post-baseline value. 
 ◦ The analysis of 3 \times ULN will contain four subsets: patients whose non-missing maximum baseline value is $\leq 1 \times$ ULN, patients whose maximum baseline is $>1 \times$ ULN but $<3 \times$ ULN, patients whose maximum baseline value is $\geq 3 \times$ ULN, and patients whose baseline values are missing. ◦ The analysis of 5 \times ULN will contain five subsets: patients whose non-missing maximum baseline value is \leq to 1 \times ULN, patients whose maximum baseline is $>1 \times$ ULN but $<3 \times$ ULN, patients whose maximum baseline is $\geq 3 \times$ ULN but $<5 \times$ ULN, patients whose maximum baseline value is $\geq 5 \times$ ULN, and patients whose baseline values are missing. ◦ The analysis of 10 \times ULN will contain six subsets: patients whose non-missing maximum baseline value is $\leq 1 \times$ ULN, patients whose maximum baseline is $>1 \times$ ULN but $<3 \times$ ULN, patients whose maximum baseline is $\geq 3 \times$ ULN but $<5 \times$ ULN, patients whose maximum baseline is $\geq 5 \times$ ULN but $<10 \times$ ULN, patients whose maximum baseline value is $\geq 10 \times$ ULN, and patients whose baseline values are missing. 	
OLT Period (Safety Population): TEAE by PT within SMQ or sub-SMQ
 
OLE Period (OLE Period Population): TEAE by PT within SMQ or sub-SMQ
 
LTE Period (LTE Safety Population): TEAE by PT within SMQ or sub-SMQ
 
Listing (Safety Population): TEAE
 
Listing (Safety Population): Elevations in hepatic laboratory tests

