
Special Safety Topic	Definition / Derivation	Analysis / Summary / Listing
	
 ○ The analysis of $20 \times \text{ULN}$ will contain seven subsets: patients whose non-missing maximum baseline value is $\leq 1 \times \text{ULN}$, patients whose maximum baseline is $>1 \times \text{ULN}$ but $<3 \times \text{ULN}$, patients whose maximum baseline is $\geq 3 \times \text{ULN}$ but $<5 \times \text{ULN}$, patients whose maximum baseline is $\geq 5 \times \text{ULN}$ but $<10 \times \text{ULN}$, patients whose maximum baseline is $\geq 10 \times \text{ULN}$ but $<20 \times \text{ULN}$, patients whose maximum baseline value is $\geq 20 \times \text{ULN}$, and patients whose baseline values are missing. ● The number and percentages of patients with a total bilirubin measurement $\geq 1.5 \times$, and $\geq 2 \times$ the Performing lab ULN during the treatment period will be summarized for all patients with a post-baseline value. 
 ○ The analysis of $1.5 \times \text{ULN}$ will contain four subsets: patients whose non-missing maximum baseline value is $\leq 1 \times \text{ULN}$, patients whose maximum baseline is $>1 \times \text{ULN}$ but $<1.5 \times \text{ULN}$, patients whose maximum baseline value is $\geq 1.5 \times \text{ULN}$, and patients whose baseline values are missing. ○ The analysis of $2 \times \text{ULN}$ will contain five subsets: patients whose non-missing maximum baseline value is $\leq 1 \times \text{ULN}$, patients whose maximum baseline is $>1 \times \text{ULN}$ but $<1.5 \times \text{ULN}$, patients whose maximum baseline is $\geq 1.5 \times \text{ULN}$ but $<2 \times \text{ULN}$, patients whose maximum baseline value is $\geq 2 \times \text{ULN}$, and patients whose baseline values are missing. ● The number and percentages of patients with an ALP measurement $>1.5 \times$ the Performing lab ULN during the treatment period will be summarized for all patients with a post-baseline value, and divided into four subsets: patients whose non-missing maximum baseline value is $\leq 1 \times \text{ULN}$, patients whose maximum baseline is $>1 \times \text{ULN}$ but $\leq 1.5 \times \text{ULN}$, patients whose maximum baseline value is $>1.5 \times \text{ULN}$, and patients whose baseline values are missing. ● The number and percentages of patients meeting the following elevated hepatic criteria: maximum ALT $\geq 3 \times \text{ULN}$ and maximum Total Bilirubin $\geq 2 \times \text{ULN}$ during the treatment period will be summarized. 
Shift tables (or scatterplots) will be produced showing the number and percentage of patients with a maximum post-baseline result in each of the categories below, by treatment group and baseline result. Note that for these tables, a single maximum baseline time point will be used. Maximum baseline will be the maximum non-missing observation in the baseline period. The maximum post-baseline value will be the maximum non-missing value from within each
	
Listing (Safety Population): Shift in hepatic laboratory tests

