
Special Safety Topic	Definition / Derivation	Analysis / Summary / Listing
	
treatment period. Scheduled visits, unscheduled visits, and repeat measurements will be included. Such shift tables will be produced for the following parameters and categories:
 
 • ALT; $\leq 1 \times \text{ULN}$, >1 to $<3 \times \text{ULN}$, ≥ 3 to $<5 \times \text{ULN}$, ≥ 5 to $<10 \times \text{ULN}$, ≥ 10 to $<20 \times \text{ULN}$, and $\geq 20 \times \text{ULN}$. • AST; $\leq 1 \times \text{ULN}$, >1 to $<3 \times \text{ULN}$, ≥ 3 to $<5 \times \text{ULN}$, ≥ 5 to $<10 \times \text{ULN}$, ≥ 10 to $<20 \times \text{ULN}$ and $\geq 20 \times \text{ULN}$. • Total bilirubin; $\leq 1 \times \text{ULN}$, >1 to $<1.5 \times \text{ULN}$, ≥ 1.5 to $<2.0 \times \text{ULN}$, $\geq 2.0 \times \text{ULN}$. • ALP; $\leq 1 \times \text{ULN}$, >1 to $\leq 1.5 \times \text{ULN}$, $>1.5 \times \text{ULN}$. 
In addition, the number and percentage of patients with maximum post-baseline results will be presented overall and by treatment group for each treatment period within the following classes:
 
 • Decreased; post-baseline category $<$ baseline category. • Increased; post-baseline category $>$ baseline category. • Same; post-baseline category $=$ baseline category. 	
	
Elevated hepatic criteria: maximum ALT $\geq 3 \times \text{ULN}$, maximum total bilirubin $\geq 2 \times \text{ULN}$.
 
Listing of patients who meet any of the following criteria:
 
 • Elevated hepatic criteria: defined as maximum ALT $\geq 3 \times \text{ULN}$, maximum total bilirubin $\geq 2 \times \text{ULN}$ • An ALT or AST $\geq 3 \times \text{ULN}$ • An ALP $\geq 1.5 \times \text{ULN}$ • A total bilirubin $\geq 2 \times \text{ULN}$ 
The listing will include: patient demographics, concomitant medications, ALT/AST/ALP/total bilirubin/GGT by visit, treatment start and stop dates, and reason for treatment discontinuation
	
Listing (Safety Population): Elevations in hepatic criteria

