	
Evaluation of Drug-Induced Serious Hepatotoxicity (eDISH) plot: To further evaluate potential hepatotoxicity, an eDISH plot will be created. Each patient with at least 1 post-baseline ALT and total bilirubin contributes 1 point to the plot. The maximum ALT measurement and the maximum total bilirubin measurement after the first injection will be included. Patients will be classified into 2 groups: never on ixekizumab or ever on ixekizumab. The measurements do not need to be taken at the same blood draw. There will only be 1 eDISH plot for each indication, regardless of treatment periods.
	
Figure (Safety Population): eDISH plot (display in Spotfire)
 
Figure (OLE Period Population): eDISH plot (display in Spotfire)
 
Figure (LTE Safety Population): eDISH plot (display in Spotfire)

Cytopenias	
Cytopenias will be defined using the PTs from the following 2 sub SMQs of the Haematopoietic cytopenias SMQ (20000027) as defined in MedDRA Version:
 
 • Broad and narrow terms in the Haematopoietic leukopenia (20000030) 	
OLT Period (Safety Population): TEAE by PT within sub-SMQ

Special Safety Topic	Definition / Derivation	Analysis / Summary / Listing
	
 Broad and narrow terms in the Haematopoietic thrombocytopenia (20000031) 
The number and percentage of patients with TEAEs will be summarized by treatment group using MedDRA PT nested within SMQ. Two summaries will be created: (1) pooling narrow and broad terms together, and (2) narrow terms only. Events will be ordered by decreasing frequency in ixekizumab group (or combined ixekizumab group in the event of multiple cohorts/doses) nested within SMQ.
	
OLE Period (OLE Period Population): TEAE by PT within sub-SMQ
 
LTE Period (LTE Safety Population): TEAE by PT within SMQ or sub-SMQ
 
Listing (Safety Population): TEAE

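### The SAP's combined liver count and eDISH plot use ALT with bilirubin only, so an AST-led case on which the protocol interrupts dosing would be missing from that count

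*SAP*

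**What the plan says.** The hepatic entry of SAP Table RHCG.6.16 (section 6.12.11) has one count that requires two liver abnormalities in the same patient. It begins "The number and percentages of patients meeting the following elevated hepatic criteria: maximum ALT" and asks for maximum ALT of at least 3 × ULN and maximum total bilirubin of at least 2 × ULN in the treatment period. The by-patient listing repeats the definition: "Elevated hepatic criteria: defined as maximum ALT", with the same thresholds. For the eDISH plot, "Each patient with at least 1 post-baseline ALT and total bilirubin contributes 1 point to the plot", and "The maximum ALT measurement and the maximum total bilirubin measurement after the first injection will be included". AST plays no part in either.

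AST does appear elsewhere in the table:
- The threshold counts begin "The number and percentages of patients with an ALT or AST measurement" and run at 3, 5, 10 and 20 × ULN.
- There is a shift table for AST.
- The listing admits anyone with ALT or AST of at least 3 × ULN, or total bilirubin of at least 2 × ULN. It shows ALT, AST, ALP, bilirubin and GGT by visit, with treatment dates and the reason for discontinuation.

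Protocol section 8.1.1 sets the interruption conditions. For normal or near-normal baseline tests (below 1.5 × ULN), one condition is "ALT or AST $>3 \times$ ULN and either TBL $>2 \times$ ULN or INR >1.5", in which case "the study drug should be interrupted and close hepatic monitoring initiate". For abnormal baseline tests the corresponding condition is "ALT or AST $>2 \times$ baseline and either TBL $>2 \times$ ULN or INR >1.5". Resumption can be considered after consultation if the tests return to baseline and a self-limited cause other than the drug is found.

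**The concern.** The protocol treats the two aminotransferases alike when it acts on a combined signal. The SAP treats them alike in its single-test counts but drops AST, without a stated reason, where the enzyme is combined with bilirubin. Single-test rows cannot show that both abnormalities occurred in one patient, so the combined row is the only summary that can. Liver biochemical change, with AST named, is an adverse event of special interest in Protocol section 9.2.2.3. What is at stake is that the combined row could read zero although a participant had dosing interrupted for a raised aminotransferase with raised bilirubin.

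**Working it through.** The plan states no figure to reproduce, so the check compares the definitions and then applies them to a case.

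| Place | Enzyme | Second condition |
|---|---|---|
| SAP combined row and listing definition | ALT ≥ 3 × ULN | bilirubin ≥ 2 × ULN |
| SAP eDISH plot | maximum ALT | maximum bilirubin |
| SAP threshold counts | ALT or AST ≥ 3, 5, 10, 20 × ULN | none |
| Protocol 8.1.1, normal baseline | ALT or AST > 3 × ULN | bilirubin > 2 × ULN or INR > 1.5 |
| Protocol 8.1.1, abnormal baseline | ALT or AST > 2 × baseline | bilirubin > 2 × ULN or INR > 1.5 |

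**Illustrative participant (assumed values).** Normal baseline, AST 4 × ULN, ALT 2.5 × ULN, bilirubin 2.5 × ULN, with ALP and INR normal and no symptoms.

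1. Protocol: 4 > 3 and 2.5 > 2, so the combined condition is met. The enzyme-only conditions (above 8 × ULN, or above 5 × ULN for more than two weeks) are not met, because 4 is below both. The combined condition alone causes the interruption.
2. SAP combined row: ALT 2.5 < 3, so the participant is not counted.
3. eDISH plot: the point sits at ALT 2.5 and bilirubin 2.5. The AST of 4 is not shown.
4. SAP single-test rows: counted under ALT or AST ≥ 3 × ULN (4 ≥ 3) and under bilirubin ≥ 2 × ULN (2.5 ≥ 2).
5. Shift tables: AST falls in the 3 to < 5 × ULN category and bilirubin in the top category.
6. Listing: the participant enters on two separate criteria, AST and bilirubin.
7. With the larger enzyme used: max(2.5, 4) = 4 ≥ 3 and 2.5 ≥ 2, so the participant would be counted.

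**How far a row using ALT or AST would follow the protocol.**
- Abnormal baseline: if the triggering enzyme itself starts at 1.5 × ULN or more, twice baseline is at least 2 × 1.5 = 3 × ULN. With bilirubin above 2 × ULN, the new row would count the case. It could miss a case only when the baseline is called abnormal because of a different test.
- INR branch: a case with INR above 1.5 and bilirubin below 2 × ULN is outside both the present row and the new one.

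**Size.** One AST-led case among the planned 80 ixekizumab participants would change the row from 0/80 = 0% to 1/80 = 1.25%. This only illustrates the scale. Neither document says how often AST leads, so no expected count can be derived.

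**The case against.** The strongest reply is that nothing is lost. The by-patient listing shows AST, bilirubin, treatment dates and the reason for discontinuation together, and in a trial of about 100 participants a safety reader would find the case there. This stands. A reader might infer that AST-led cases would go unreported, and the documents do not support that. The gap is confined to one summary row and one plot axis.

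A second reply is that a management trigger is not an analysis definition. Nothing requires the SAP to mirror the interruption rule, which has enzyme-only, symptom, ALP and INR conditions as well. This also stands, and it limits the aim to adding a useful count rather than reproducing the rule.

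A third is that ALT alone may be deliberate. SAP section 6.12 says that the safety analyses follow compound-level standards, and section 6.12.11 lets a program safety analysis plan, which is not among the documents, supersede the special-topic analyses. The protocol's thresholds for additional hepatic data collection (section 9.4.11.1) also name ALT and not AST. ALT may be preferred as the more liver-specific enzyme. A reader might conclude that the ALT criterion and axis are errors to be replaced, but the documents do not show that. These points argue for keeping the ALT versions. They do not explain why AST is accepted in the threshold counts and left out of the combined one, and an added row disturbs no standard.

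**Conclusion.** The mismatch is real and narrow. An AST-led case with raised bilirubin can meet a protocol interruption condition and be absent from the SAP's only combined liver count, while remaining visible in the single-test rows, the shift tables and the listing. The effect is a possible undercount in one descriptive safety row. No decision rule or primary conclusion depends on it.

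Three further inferences should be avoided:
- The protocol action is interruption with conditional resumption, so such a case is not necessarily a permanent discontinuation.
- The SAP draws no cut-lines or quadrants on the eDISH plot. All that can be said is that the point is placed by its ALT.
- No expected number of cases can be stated.

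The conclusion rests on the text of the two documents. It assumes that the program safety analysis plan does not already supply a combined count using AST.

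**What to change.** In SAP Table RHCG.6.16:
- Keep the ALT-only combined row. Beside it add a row for maximum ALT or AST of at least 3 × ULN with maximum total bilirubin of at least 2 × ULN, and a matching flag in the by-patient listing.
- Keep the ALT-based eDISH plot and add an AST version as a supplement.
- Note under the new row that it does not reproduce the interruption rule, because the INR branch is not included.

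The cost is one derived variable, one row, one flag and one figure. ALT, AST and bilirubin are all in the chemistry panel of Protocol Appendix 2, so no data collection changes. SAP section 6.12.11 allows the change to be recorded in the program safety analysis plan without a SAP amendment.

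The downside is that AST of non-hepatic origin may add a case. That can be checked against the listing and against creatine kinase, which is in the same panel. Creatine kinase is not among the stated contents of the hepatic listing, so it would be read from the general laboratory listing or added. No clinical rule changes.

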5.1. Overall Design

Study I1F-MC-RHCG (RHCG) is a multicenter, open-label, Phase 3 study of ixekizumab with adalimumab as a randomized reference arm in participants with JIA categories of ERA (including JoAS) and JPsA from 2 to less than 18 years of age, who are bDMARD-naive or bDMARD-IR as per investigator's judgement.

The study will be conducted in 5 parts, which includes screening and post-treatment follow up (PTFU) periods, in a 5-year study. The open-label treatment (OLT) period will include the OLT with ixekizumab or adalimumab up to Week 16. The open-label extension (OLE) period will provide OLT with ixekizumab or adalimumab up to Week 104. The LTE will provide OLT with ixekizumab only. The total study duration will include the screening period, 5-year treatment period, and PTFU period. Out of 100 participants, 40 will be randomly assigned into 1:1 ratio among naive bDMARD participants either to treatment arm (ixekizumab) or reference arm (adalimumab), and the remaining 60 participants will be randomly allocated either to naive or bDMARD-IR group at Visit 2 (Week 1). Participants receiving ixekizumab during the OLT period will continue to receive ixekizumab during the OLE period. Participants receiving adalimumab during the OLT period who did NOT attain a JIA ACR 30 response at Week 16 will be switched to ixekizumab in the OLE period. Participants receiving adalimumab during the OLT period who did attain a JIA ACR 30 response at Week 16 will be given the option to switch or not to switch to ixekizumab in the OLE period. The decision to switch for participants who achieved a JIA ACR 30 response at Week 16 will be left to the participant/participant's caregiver and investigator. A switch from adalimumab to ixekizumab during the OLE period may also occur at any other visit after Week 16 based on the participant/participant's caregiver and investigator's decision. After switching to ixekizumab, the participants will not have the option to resume adalimumab treatment during the remainder of the trial participation.

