5.1.3. Open-Label Extension Period

In the OLE period, all participants who were receiving ixekizumab in the OLT period will continue to receive ixekizumab for approximately 88 weeks.

Participants receiving adalimumab during the OLT period who did NOT attain a JIA ACR 30 response at Week 16 will be switched to ixekizumab in the OLE period. Participants receiving adalimumab during the OLT period who did attain a JIA ACR 30 response at Week 16 will be given the option to switch or not to switch to ixekizumab in the OLE period. Participants who are switched over to ixekizumab treatment after the OLT period will be treated as a separate group. The decision to switch for participants who achieved a JIA ACR 30 response will be left to the participant/participant's caregiver and investigator. A switch from adalimumab to ixekizumab during the OLE period may also occur at any other visit after Week 16 based on the participant/participant's caregiver and investigator's decision. For switching participants, the first ixekizumab dose can occur at any study visit during OLE period and after a minimum of 2 weeks after the last adalimumab dose (e.g., the subject that received the last dose of adalimumab at Week 14 will receive the first dose of ixekizumab at Week 16).

Switching from adalimumab to ixekizumab for a safety reason requires a washout period of sufficient length to allow the safety issue/parameter to resolve.

The participants switching to ixekizumab will not receive the starting ixekizumab dose but will receive the appropriate regular ixekizumab dose according to their weight at each visit. After switching to ixekizumab, the participants will not have the option to resume adalimumab treatment during the remainder of the trial participation. Rationale/justification for switching will be captured for any participant switching to ixekizumab and recorded in the participant's case report form.

Weight will be recorded, and dosing of ixekizumab and adalimumab will be adjusted during the OLE period according to the participant's weight at each visit.

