6.1.2.1. General Considerations for the OLT Period

The OLT period starts at the first injection of study treatment at Week 0 (Visit 2) and ends prior to the first injection of study treatment at Week 16 (Visit 7) or the ETV (between Weeks 0 and 16). Efficacy and health outcomes data collected in the OLT period will be summarized for intent-to-treat (ITT) population without inferential statistics.

Efficacy baseline will be defined as the last available value on or before the first injection at Week 0 (Visit 2) for efficacy and health outcomes. In most cases, this will be the measure recorded at Week 0 (Visit 2). For efficacy measures, if the patient does not take any injection, the last available value on or prior to randomization date will be used.

For safety analyses using a baseline period, the baseline period is defined as the time from Visit 1 to the date/time of the first injection at Week 0 (Visit 2).

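### The SAP's eDISH rule can plot an adalimumab switcher's adalimumab-time ALT or bilirubin maximum in the ixekizumab group, because the window does not restart at the switch

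*SAP*

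**What the plan says.** The rule stands in the Hepatic row of SAP Table RHCG.6.16 (section 6.12.11). It has five parts:

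- **Window:** "The maximum ALT measurement and the maximum total bilirubin measurement after the first injection will be included".
- **Pairing:** "The measurements do not need to be taken at the same blood draw".
- **Grouping:** "Patients will be classified into 2 groups: never on ixekizumab or ever on ixekizumab".
- **Number of plots:** "There will only be 1 eDISH plot for each indication, regardless of treatment periods".
- **Display column of the same row:** three eDISH figures, one each for the Safety, OLE Period and LTE Safety populations.

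Switching is part of the design. Protocol 5.1 states: "Participants receiving adalimumab during the OLT period who did NOT attain a JIA ACR 30 response at Week 16 will be switched to ixekizumab". Week 16 responders on adalimumab may switch then or at any later visit. Anyone still on adalimumab who enters the LTE is moved to ixekizumab at Week 104 (Protocol 5.1; SAP 5.1).

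**The concern.** The grouping looks at the whole study, and so does the measurement window. A child who takes adalimumab for 16 to 104 weeks and then ixekizumab is filed under ixekizumab, but the plotted maxima may date from the adalimumab weeks. The two coordinates may also come from different drugs, for example an ALT peak on adalimumab and a bilirubin peak on ixekizumab.

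An eDISH plot is read by asking which drug the points in the upper right belong to. Liver enzyme change is an adverse event of special interest for ixekizumab (Protocol 9.2.2.3). A figure that can credit the reference drug's values to the test drug, while taking patients out of a reference group of about 20, does not answer that question cleanly.

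**Working it through.** The plan states no figure for this plot, so there is none to reproduce. The check is a reading of the rule, followed by arithmetic on its possible reach.

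**1. Which injection starts the window?** The eDISH text does not name the drug. Three things point to the first injection of either study drug:

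- The same window must serve patients who never receive ixekizumab.
- SAP 6.1.2.1 ties the term to Week 0 for both arms: "the baseline period is defined as the time from Visit 1 to the date/time of the first injection at Week 0 (Visit 2".
- Where the SAP wants the clock to restart, it says so. The switcher safety baseline (6.1.2.2.2) and the immunogenicity baseline (6.12.12.1.3) both name the first ixekizumab injection. The eDISH rule has no such wording.

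**2. Would period-specific figures repair it?** Suppose the three listed figures are meant by period.

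- In an OLT figure, later switchers carry the ever-ixekizumab label although all their OLT values are on adalimumab.
- In an OLE Period Population figure, SAP 6.1.2.2.1 keeps only pre-switch data for switchers, so their points are again adalimumab values under the ixekizumab label.
- In an LTE figure all values are on ixekizumab, but everyone has taken it, so the never group is empty by definition.

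**3. How many patients does the rule reach?** SAP 5.2 assigns 80 to ixekizumab and 20 to adalimumab. For mandatory Week 16 switchers I assume a 71% response, borrowed from the Week 12 JIA ACR30 rate in the ERA trial described in Protocol 3.2: 20 × (1 − 0.71) = 5.8, about 6. At response rates of 80% to 60% the number is 4 to 8. The ceiling is all 20.

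Share of the ever-ixekizumab group = s / (80 + s); patients left in the never group = 20 − s.

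| Switchers s | Share of ever group | Left in never group |
|---|---|---|
| 6 | 6/86 = 7.0% | 14 |
| 10 | 10/90 = 11.1% | 10 |
| 15 | 15/95 = 15.8% | 5 |
| 20 | 20/100 = 20.0% | 0 |

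**4. How often would the plotted maximum be an adalimumab value?** Protocol Appendix 7 schedules these post-baseline chemistry draws: 2 in OLT (V4, V7), 7 in OLE (V11 to V29) and 14 in LTE (V30 to V69), 23 in all. The V7 and V29 draws are counted as adalimumab time for patients who switch at those visits. If draws are exchangeable, the chance that the ALT maximum falls on adalimumab is the share of draws taken on adalimumab, p. If the ALT and bilirubin maxima are also independent, the chance for at least one coordinate is 1 − (1 − p)².

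| Switch and follow-up | p for ALT | At least one coordinate |
|---|---|---|
| Week 16, followed to Week 264 | 2/23 = 8.7% | 16.6% |
| Week 16, data end at Week 104 | 2/9 = 22.2% | 39.5% |
| Week 104, followed to Week 264 | 9/23 = 39.1% | 62.9% |

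**5. Expected misplaced ALT maxima.** With 6 switchers at Week 16 and 14 at Week 104: 6 × 2/23 + 14 × 9/23 = 138/23 = 6.0, or 6 of 100 points in the ever group. With 6 switchers at Week 16 only: 12/23 = 0.5.

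**The case against.** The strongest reply is that this plot is supplementary and that the attributable liver analyses are elsewhere. That is right. The same row of the SAP table summarises ALT, AST, bilirubin and ALP elevations, and the joint ALT and bilirubin criterion, within the treatment period. Its shift tables take maxima from within each period. Its listing of patients who meet the hepatic criteria shows liver tests by visit with treatment start and stop dates. Any clinically relevant point can therefore be traced to the drug being taken. The group label is also literally true for switchers, no inferential comparison between arms is planned, and the misattribution runs against ixekizumab: the plotted value is never lower than the ixekizumab-time maximum. These facts limit the harm. They leave the figure itself wrong as a display by drug.

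A reader might infer two stronger things that the documents do not support.

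- **That most adalimumab liver maxima will be shown as ixekizumab findings.** If 15 to 20 of 20 patients switch, 75% to 100% of them have adalimumab-time values eligible for plotting. A value is plotted only if it exceeds everything measured later, and most such maxima need not be abnormal.
- **That liver events on adalimumab are themselves a route into the ixekizumab group.** Protocol 5.1.3 does provide for such switches: "Switching from adalimumab to ixekizumab for a safety reason requires a washout period of sufficient length". But the sentence goes on to require that the safety issue resolve. Protocol 8.1.1 interrupts study drug at stated liver thresholds and discontinues it unless tests return to baseline and a self-limited non-drug cause is found. The text does not expressly bar a later switch, but it gives no basis for counting such cases.

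**Conclusion.** The point holds as one of attribution in a single safety figure. As written, an adalimumab-time maximum can be plotted in the ixekizumab group, and maxima from the two drugs can be combined in one point. Switchers would form 7% to 20% of the ever-ixekizumab group if 6 to 20 of 20 switch, and the never group would shrink to between 14 and 0. The lower end rests on the borrowed 71% rate. Only a minority of switchers would have a pre-switch ALT maximum plotted, about 9% to 39% over full follow-up. Those percentages rest on exchangeable scheduled draws and ignore unscheduled hepatic monitoring.

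Reading the first injection as that of either drug is an inference, though the natural one. If the sponsor meant the first ixekizumab injection for switchers, the SAP needs to say so. The conflict between one plot and three figures does not depend on that reading. The primary efficacy analysis is unaffected.

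**What to change.** Redefine the eDISH maxima by drug exposure in SAP Table RHCG.6.16:

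- In the ixekizumab group, use only values after the first ixekizumab injection, for switchers and for patients assigned to it from Week 0.
- Plot adalimumab-time maxima, including switchers' pre-switch values, as a separate adalimumab group or symbol.
- Take both coordinates of a point from the same drug's exposure time.
- State whether there is one plot or one per population, and make the definition and display columns agree.

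With this rule no point in the ixekizumab group rests on an adalimumab-time value. The cost is one SAP paragraph and a date filter in the program. The downside is that switchers contribute two points, so the rule of one point per patient must be reworded and the figure should carry a footnote saying so.
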